11.3.11 Worst Post-baseline Bleeding Grade (WHO Bleeding Scale)

Population: Full Analysis Set, Per Protocol Set (for Core Phase only)

Target Phases: Core Phase, Extension Phase

Analysis items: - The worst post-baseline bleeding grade based on WHO Bleeding Scale

Contents: - The number and proportion of subjects with the worst post-baseline bleeding grade (WHO Bleeding Scale) reported in Core Phase (up to End of Study visit (excluding dose tapering and follow-up period)) and in Extension Phase (from E1 (Month 1) to Last Visit).

Definitions: - WHO Bleeding Scale:
 Grade 0: No bleeding
 Grade 1: Petechial bleeding
 Grade 2: Mild blood loss (clinically significant)
 Grade 3: Gross blood loss
 Grade 4: Debilitating blood loss.
- Worst post-baseline bleeding grade (WHO Bleeding Scale) is the highest grade reported after baseline.
- The denominator is the number of subjects in the analysis population.

12 Pharmacokinetic Concentrations

Blood samples for serial PK assessments will be collected during Visit 5 (Week 2) and Visit 10 (Week 10) of the Core Phase. Regardless of the subject's current treatment regimen (e.g., once daily, three times a week), the serial PK sampling at Visit 5 (Week 2) and Visit 10 (Week 10) must occur on a day the subject is scheduled to take their dose of study drug. Therefore, if study drug has been held or the dosing regimen has changed within the past week, the serial PK samples should be collected at a visit later than Visit 5 (Week 2) or Visit 10 (Week 10). This is to ensure that serial PK samples will be obtained when the subject has been on a stable dose for at least 1 week.

During the serial PK sampling visits, subjects will have three blood samples (2 mL each) drawn: pre-dose; between 2 and 4 hours post-dose; and between 6 and 8 hours post-dose.

Blood samples for sparse PK assessments (2 mL each) will be collected while the subject is at the clinic during Visit 4 (Day 8), Visit 7 (Week 4), Visit 8 (Week 6), Visit 13 (Week 16) and Visit 22 (Week 26)/End of Treatment (EOT) (2 mL each).

The pharmacokinetic sampling schedule is presented in following table:

| Study Day | Sparse/Serial | Sampling Times |
|---------------------------|---------------|--|
| Visit 4 (Day 8) | Sparse | During clinic visit |
| Visit 5 (Week 2) | Serial | 
 • Pre-dose • Between 2 and 4 hours post-dose • Between 6 and 8 hours post-dose |
| Visit 7 (Week 4) | Sparse | During clinic visit |
| Visit 8 (Week 6) | Sparse | During clinic visit |
| Visit 10 (Week 10) | Serial | 
 • Pre-dose • Between 2 and 4 hours post-dose • Between 6 and 8 hours post-dose |
| Visit 13 (Week 16) | Sparse | During clinic visit |
| Visit 22 (Week 26) | Sparse | During clinic visit |

The data handling methods for Pharmacokinetic Concentrations are presented below:

1) Data Handling for Below the Lower Limit of Quantification (BLQ)

If the recorded plasma avatrombopag concentration is below the limit of quantification (BLQ), the measured value of the concentration will be treated as the following:

- For tables, BLQ will be substituted by 0.
- For listings, display BLQ as “BLQ”.

2) Data Handling for Missing Value

If missing data is recorded for plasma avatrombopag concentration, imputation of the records will not be performed. Thus, any missing records for plasma avatrombopag concentration will be excluded from analysis.

If blood concentration is not measured (not done) then it is considered as missing.

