## 6.4.4 Study Drug Dose-Adjustment Guidelines

In accordance with approved overseas labeling, dose and dosage adjustments will target maintaining the platelet count  $\geq 50 \times 10^9 / L$  and  $< 200 \times 10^9 / L$  and follow the dose-adjustment guidelines presented in Table 1 and Table 2. All subjects will initiate treatment at 20 mg once daily (Dose Level 4).

Investigators must consider dose and dosage titration in accordance with a subject's platelet count every 2 weeks. However, dose titration may be performed weekly for subjects with platelet counts  $<50\times10^9/L$  or  $>400\times10^9/L$ .

**Table 1** Avatrombopag Dose Levels for Titration

Dose*	Level
40 mg Once Daily	6
40 mg Three Times a Week AND 20 mg on the Four Remaining Days of Each Week	5
20 mg Once Daily	4
20 mg Three Times a Week	3
20 mg Twice a Week OR 40 mg Once Weekly	2
20 mg Once Weekly	1

\* Subjects taking avatrombopag less frequently than once daily should take the medication in a consistent manner from week to week.

**Table 2** Avatrombopag Dose Adjustments

Platelet Count (× 10  /L)	Dose Adjustment or Action
<50 after at least 2	Increase One Dose Level per Table 1.
weeks of Avatrombopag	• Wait 2 weeks to assess the effects of this regimen and any subsequent dose adjustments.
≥50 to <200	Keep on the current dose and dosage
≥200 to ≤400	Decrease One Dose Level per Table 1.
	• Wait 2 weeks to assess the effects of this regimen and any subsequent dose adjustments.
>400	Stop Avatrombopag.
	Increase platelet monitoring to twice weekly.
	• When platelet count is less than 150×10  /L, decrease One Dose Level per Table 1 and reinitiate therapy.
<50 after 4 weeks of 40 mg Avatrombopag once daily	Discontinue Avatrombopag.
>400 after 2 weeks of 20 mg Avatrombopag weekly	Discontinue Avatrombopag.

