8.3 Analysis Methods

8.3.1 Descriptive Statistics

Descriptive statistics:

| | |
|--------------------------------|--|
| Continuous data except for PK | PK concentration data |
| The number of subjects (N) | The number of subjects (N) |
| Arithmetic Mean | Arithmetic Mean |
| Standard Deviation (SD) | Standard Deviation (SD) |
| Median | Median |
| Minimum and Maximum | Minimum and Maximum |
| First quartile, Third quartile | - |
| - | The number and % of BLQ |
| | Coefficient of variation (CV%) for arithmetic mean |
| - | Geometric Mean |
| - | 95% confidence interval (CI) of geometric mean |
| - | Geometric CV% |

CV%, Geometric mean, 95% CI of geometric mean, and Geometric CV% are calculated using the following formula:

CV(%) = (standard deviation) / (arithmetic mean) × 100

$$\text{Geometric mean} = \exp \left[\frac{\sum_{i=1}^n \log X_i}{n} \right] = \sqrt[n]{\prod_{i=1}^n X_i}$$

95% CI of geometric mean = $\exp(\mu \pm 1.96 \cdot s/\sqrt{n})$

μ : mean on the natural logarithm scale

s: standard error on the natural logarithm scale

$$\text{Geometric CV(%) = } \sqrt{\exp(s^2) - 1} \times 100$$

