12.1 Summary of Avatrombopag Concentrations

Population: Full Analysis Set

Target Phases: Core Phase

Analysis items: - Avatrombopag concentrations in plasma

Visits: - Visit 5 (Week 2), Visit 10 (Week 10): Pre-dose, Between 2 and 4 hours postdose, Between 6 and 8 hours postdose.
- Visit 4 (Day 8), Visit 7 (Week 4), Visit 8 (Week 6), Visit 13 (Week 16), Visit 22 (Week 26).

Contents: - Calculate the descriptive statistics of avatrombopag concentrations in plasma by analysis visits/time points.

Definitions: - Regarding summary statistics of avatrombopag concentrations, refer to [8.3.1 Descriptive Statistics](#).

13 Safety Analyses

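### Setting below-quantification (BLQ) concentrations to 0 conflicts with the log-scale statistics that the SAP requires: one BLQ value at a time point leaves no valid geometric mean, CI or geometric CV%

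*SAP*

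**What the plan says.** Three parts of the SAP meet here.

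- **Section 12, data handling for BLQ:** "For tables, BLQ will be substituted by 0". Listings show the BLQ flag instead. The next item excludes missing concentrations from analysis; BLQ values are not treated as missing.
- **Section 12.1:** "Calculate the descriptive statistics of avatrombopag concentrations in plasma by analysis visits/time points". For the choice of statistics it says "Regarding summary statistics of avatrombopag concentrations, refer to" section 8.3.1.
- **Section 8.3.1:** the list for PK concentrations includes the number and percentage of BLQ values, the geometric mean, the "95% confidence interval (CI) of geometric mean" and the geometric CV%. It adds: "CV%, Geometric mean, 95% CI of geometric mean, and Geometric CV% are calculated using the following formula". The geometric mean is written as the exponential of the mean log value and, equivalently, as the n-th root of the product, over all n values.

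Section 8.4.1 sets the display of the geometric mean and its CI to three significant digits. It has no provision for a statistic that cannot be calculated.

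**The concern.** A zero has no logarithm. The SAP places zeros in the concentration tables and then asks for three statistics that need the logarithm of every value in those tables. It gives no separate substitution for the log-scale statistics, no instruction to exclude BLQ values from them and no not-calculated rule. The SAP provides for BLQ values, since it counts them in the same table.

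The programmer would then have to improvise. The row could show 0, a blank, or a geometric mean from the positive values only, set beside an N and an arithmetic mean that include the zeros. In the last case the statistics in one row describe different sets of samples, and the geometric mean is too high for the full set. Japanese exposure data are a stated exploratory objective (Protocol 2.1.3, SAP 3.1.3), and section 12.1 is the SAP's only concentration summary.

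**Working it through.** The documents state no figure on this point, so there is none to reproduce. The check applies the SAP 8.3.1 formulas to values that contain zeros.

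**Inputs from the documents:** BLQ = 0 in tables (SAP 12); geometric mean = exp(Σ log Xᵢ / n) = (Π Xᵢ)^(1/n) (SAP 8.3.1); about 19 subjects (Protocol 4.1).

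**Assumptions, not in the documents:** the concentrations, the number of BLQ values and the LLOQ.

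**Step 1. One zero among n values.**
- Product form: (0 × …)^(1/n) = 0.
- Log form: log 0 is undefined. So are the log-scale mean and SD, and with them the CI and the geometric CV%.
- The two expressions that 8.3.1 equates no longer agree. No assumed concentration is needed for this step.

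**Step 2. Simple example: 15 values of 100 ng/mL and 4 BLQ.**
- Arithmetic mean under the SAP: 15 × 100 / 19 = 78.9.
- Geometric mean: 0 (product form), undefined (log form), or 100 if zeros are dropped.
- BLQ = LLOQ/2 with LLOQ 1: exp[(15 × 4.605 + 4 × (−0.693)) / 19] = exp(66.305 / 19) = 32.8.
- BLQ = LLOQ/2 with LLOQ 5: exp[(69.078 + 4 × 0.916) / 19] = exp(72.743 / 19) = 46.0.

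This example has no spread among the measurable values, so it is extreme. A geometric mean above the arithmetic mean is impossible for a single data set, but here it is forced by the construction.

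**Step 3. Example with spread: 19 lognormal quantiles, geometric mean 50, geometric CV about 80%, lowest values treated as BLQ.**

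| BLQ of 19 | Arithmetic mean, zeros kept | Geometric mean, SAP product form | Geometric mean, zeros dropped |
|---|---|---|---|
| 0 | 62.7 | 50.0 | 50.0 |
| 1 | 62.1 | 0 | 53.9 |
| 2 | 61.1 | 0 | 57.4 |
| 4 | 58.5 | 0 | 64.3 |

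Dropping zeros biases the geometric mean upward in every BLQ row. The impossible ordering against the arithmetic mean appears at 4 BLQ, not at 1 or 2. The set shows direction only: the values labelled BLQ (about 13 to 27) lie well above an LLOQ of 1 or 5.

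**Step 4. How often one BLQ would occur.** Chance of at least one among 19 = 1 − (1 − p)^19, assuming independent samples with BLQ probability p: 17% at p = 1%, 32% at 2%, 62% at 5%, 86% at 10%. The documents do not give p.

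**Step 5. Where BLQ is more plausible.**
- Protocol 6.4.4 allows regimens down to "20 mg Once Weekly", so a pre-dose sample can follow the last dose by 7 days.
- Sparse samples are not tied to time since dose. The deferral after a hold or regimen change is stated only for serial samples (Protocol 8.3, SAP 12).
- Subjects who stop treatment complete the EOT assessments if possible (Protocol 5.3.1). These include a sparse PK sample (Protocol 7.2.5).

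**The case against.** The formula conflict is not disputed; the objections concern likelihood, mechanism and importance.

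- **Likelihood.** A reader might infer that trough samples will yield BLQ values and hence wrong geometric means. The documents do not support that: they give no LLOQ, half-life or BLQ rate, and tabulating BLQ counts provides for such values without predicting them. Serial samples are deferred if drug was held or the regimen changed in the past week. All subjects start on daily dosing at Level 4, and Level 1 is three one-level reductions away, so a 7-day gap is not realistic at Visit 4 (Day 8) or Visit 5 (Week 2). This objection stands, and the point must be conditional.
- **Mechanism.** A reader might infer that SAS will silently discard the zeros. Appendix 1 of the SAP has code for CIs of proportions and means, none for geometric statistics. Dropping is one possible result. The BLQ count in the same table would also alert a careful reader. This stands too, but the other results, 0 or not computable, are no better.
- **Importance.** Population PK has its own analysis plan (SAP 5.3). The arithmetic mean, median, minimum and maximum remain computable, and individual concentrations are listed. No efficacy or safety conclusion depends on these tables. This stands and limits the severity.
- **Remedy.** LLOQ/2 is one convention among several, and the result is sensitive to it: 46.0 against 32.8 in Step 2 is a 40% difference. That is a reason to fix a rule in advance, not to leave it open.

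**Conclusion.** The point holds as a minor, conditional defect. At any time point with at least one BLQ value, the SAP's own rules give a geometric mean that is 0 or undefined, and a CI and geometric CV% that cannot be computed. That follows from the formulas alone. If zeros are dropped, the geometric mean is biased upward relative to the full set of samples. The size of that bias cannot be stated from the documents; the figures above rest on assumed concentrations.

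Whether and where BLQ occurs is not shown. It is more plausible at later pre-dose samples on less-than-daily regimens, and at sparse or EOT samples taken after a hold or stop. The documents do not support a reading that the exploratory PK objective is compromised: the scope is the descriptive concentration tables.

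**What to change.** In SAP section 12, restrict the zero substitution to the arithmetic statistics and state one rule for the geometric mean, its CI and the geometric CV%. One workable rule is BLQ = LLOQ/2 for these three, shown as NC (not calculated) when more than half of the values at a time point are BLQ. Another stated BLQ share for NC, or a censored-likelihood estimate, would also serve. Footnote the rule and the number of BLQ values in the table.

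The cost is about two sentences in the SAP and one line of programming, with no change to study conduct. The downside is that the geometric mean can depend noticeably on the substitution when several values are BLQ (32.8 at LLOQ 1 against 46.0 at LLOQ 5 with 4 of 19 BLQ), so the rule should be settled before database lock.

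Section 8.3.1 needs a separate correction at the same time: it defines "s: standard error on the natural logarithm scale", yet divides s by √n in the CI and squares it in the geometric CV%. Both formulas need the log-scale standard deviation. Correcting that does not resolve the zero problem.

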12.1 Summary of Avatrombopag Concentrations

Population: Full Analysis Set

Target Phases: Core Phase

Analysis items: - Avatrombopag concentrations in plasma

Visits: - Visit 5 (Week 2), Visit 10 (Week 10): Pre-dose, Between 2 and 4 hours postdose, Between 6 and 8 hours postdose.
- Visit 4 (Day 8), Visit 7 (Week 4), Visit 8 (Week 6), Visit 13 (Week 16), Visit 22 (Week 26).

Contents: - Calculate the descriptive statistics of avatrombopag concentrations in plasma by analysis visits/time points.

Definitions: - Regarding summary statistics of avatrombopag concentrations, refer to [8.3.1 Descriptive Statistics](#).

13 Safety Analyses

13.1 Drug Exposure

Population: Safety Set

Target Phases: Core Phase, Core Phase and Extension Phase

Analysis Items: - Duration of treatment (week), Total actual dose (mg), Total planned dose (mg), Average weekly dose (mg/week), Compliance rate (%)

Contents: - The descriptive statistics for Core Phase and Extension Phase are calculated separately as below:

- Core Phase: Duration of treatment (week), Total planned dose (mg).
- Extension Phase: Duration of treatment (week), Total actual dose (mg), Total planned dose (mg), Average weekly dose (mg/week), Compliance rate (%).

- The number and proportion of subjects in subcategories of Duration of treatment (week), Average weekly dose (mg/week), and Compliance rate (%) as below are calculated:

- Any exposure, n

- Core Phase:

- ≥ 6 weeks
- ≥ 18 weeks
- ≥ 26 weeks

- Core Phase and Extension Phase:

- ≥ 6 weeks
- ≥ 18 weeks
- ≥ 26 weeks
- ≥ 32 weeks
- ≥ 52 weeks
- ≥ 122 weeks
- ≥ 126 weeks

- Average weekly dose (mg/week):

- <60 mg
- $60 \leq - < 120$ mg
- $120 \leq - < 160$ mg
- ≥ 160 mg

- Compliance rate (%):

- <90
- $90 \leq - < 110$
- ≥ 110

Definitions:

- Duration of treatment (week) = (the last treatment day – the first treatment day + 1) / 7
- Total actual dose (mg) = Sum of (Tablets dispensed amount – Tablets returned amount – Tablets lost amount) * 20
- Total planned dose (mg) = Sum of ((Regimen end date in each regimen duration – Regimen start date in each regimen duration + 1) * Daily dose^a)

^a: Daily dose is calculated by using dose description, dose unit and dosing frequency. For Core Phase, calculate total planned dose until the last dose date of Core Phase.

- Average weekly dose (mg/week) = Total actual dose (mg) / Duration of treatment (week)
- Compliance rate (%) = (Total actual dose / Total planned dose) * 100

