## 7.2.5 Visit 22/Week 26: End of Treatment

- Collect vital signs (blood pressure and pulse). Vital signs should be taken after sitting for 5 minutes whenever possible. Vital signs should be taken prior to any blood draws.
- Collect platelet counts via local lab.
- Collect blood for central laboratory tests (see Section 9.7).
- Perform Sparse PK sampling.
- Perform pregnancy test for female subjects of childbearing potential Urine or serum pregnancy test should be performed.

- Perform WHO Bleeding Scale Assessment (Appendix C). The Investigator should ask the subject the following question: "Have you experienced any bruising or bleeding since the last visit?"
- Dispense study drug, if applicable, and review administration instructions.
- Retrieve unused medication, as needed, and review subject dosing diary to record compliance.
- Dispense new diary.
- Perform physical exam.
- Review and record AEs that may have occurred since the previous visit.
- Record any use of rescue medication since the previous visit.
- Record concomitant medications and procedures.
- For subjects who are willing and able to enter the Extension Phase, review all inclusion and exclusion criteria to confirm subject eligibility. Subjects entering directly into the Extension Phase will not enter the Dose-tapering and Follow-up Periods of the Core Study.

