7.3 Per Protocol Set (PPS)

The Core Phase PPS will include all enrolled subjects who receive protocol-assigned study drug and who do not meet any pre-specified criteria. A comprehensive list of criteria for exclusion from the PPS will be agreed upon by the study team and documented prior to database lock.

Examples of these criteria may include:

- Use of certain prohibited concomitant medications
- Selected Inclusion/Exclusion criteria not met for the Core Phase
- Lack of compliance with study medication during the Core Phase

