*: Item “Subjects who are ongoing in the extension phase” only exists in the first analysis (after the last patient completes the Core Phase).

If a subject has multiple discontinuation reasons, they will be counted for each individual discontinuation reason.

Definitions: For each of the following items, the denominator is defined as noted below.
Core Phase

| Items | The denominator of percentage |
|--|--|
| 
 • Enrolled into core phase study • Completed the core phase study • Discontinued the core phase study • Reason for discontinuation • Completed the core phase treatment • Prematurely discontinued the core phase treatment • Reason for discontinuation | The number of subjects in Safety Set of Core Phase |

Extension Phase

| Items | The denominator of percentage |
|--|---|
| 
 • Entered the Extension Phase • Treated with study drug • Not treated with study drug • Completed study • Discontinued the study • Reasons for discontinuation of study | The number of subjects in Safety Set of Extension Phase |

| | |
|---|--|
| 
 • Ongoing in the extension phase • Completed the treatment • Discontinued the treatment • Reasons for discontinuation of treatment | |
|---|--|

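### SAP 13.1 gives the actual dose no cut-off matching the planned dose or treatment duration, so compliance rate and average weekly dose can divide quantities from different periods

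*SAP*

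**What the plan says.** SAP 13.1 (Drug Exposure) defines the dose taken by tablet accountability: "Total actual dose (mg) = Sum of (Tablets dispensed amount – Tablets returned amount – Tablets lost amount) * 20". Two results use it: "Compliance rate (%) = (Total actual dose / Total planned dose) * 100", and average weekly dose, which is total actual dose over duration of treatment in weeks. The footnote to planned dose sets an end point: "For Core Phase, calculate total planned dose until the last dose date of Core Phase". No end point is given for the actual dose, and no rule says which phase a given supply belongs to.

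The Core descriptive statistics in the same section are limited to two items: "Core Phase: Duration of treatment (week), Total planned dose (mg"). Actual dose, weekly dose and compliance appear on the Extension line. The categories for weekly dose and compliance name no phase, and the section's target phases are Core and the two phases combined. Listing 16.2.5.4 (SAP 14) covers compliance in both phases.

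Visit 22 is a Core visit with drug dispensing (Protocol 7.2.5 and Appendix A): "Dispense study drug, if applicable, and review administration instructions". The next visit for a subject who continues is E1 at Month 1 (Protocol 7.3.1 and Appendix B). SAP 5.4 plans one analysis when the last patient completes the Core Phase. SAP 9.2 expects ongoing Extension subjects at that point, since its row for them "only exists in the first analysis (after the last patient completes the Core Phase").

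**The concern.** Dispensed minus returned minus lost equals tablets taken only once a supply has been reconciled. Until then, tablets in the subject's hands count as swallowed. This matters in two places.

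- **Ongoing subjects at the first analysis.** The supply from the last visit has been dispensed and not yet returned, so it enters the actual dose in full. Planned dose and duration run only over time already elapsed.
- **The Core/Extension boundary.** There is no Extension visit between Visit 22 and E1, so the tablets for the first Extension month come from Visit 22. A program that assigns tablets by dispensing visit books them to Core, while the doses themselves are planned in the Extension.

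At stake are compliance and average weekly dose, which give the dosing context for safety. Safety is a secondary objective of the Core Phase and the primary objective of the Extension. A compliance criterion is also an example of a PPS exclusion in SAP 7.3: "Lack of compliance with study medication during the Core Phase".

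**Working it through.** The documents state no compliance or weekly-dose result, so there is no figure to reproduce first.

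**Inputs**
- Core length: 26 weeks = 182 days (Protocol 1.5).
- Extension visits: monthly (Protocol 7.3.1), window ±7 days (Appendix B). Month length taken as 30.4 days.
- Outstanding supply S, in days: not in the documents. Assumed 30, range 28 to 37 (37 = 30 plus the 7-day window).
- Subject: fully adherent, constant regimen. Worked regimen: 20 mg once daily (Level 4) = 140 mg/week.

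**1. Ongoing at the first analysis, combined phases.** Just after the visit at Extension month k, with a full supply outstanding:

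compliance = (182 + 30.4k + S) / (182 + 30.4k)

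| k | days elapsed | S = 30 | S = 28 | S = 37 |
|---|---|---|---|---|
| 0 (just after Visit 22) | 182 | 212/182 = 116.5% | 115.4% | 120.3% |
| 3 | 273.2 | 303.2/273.2 = 111.0% | 110.2% | 113.5% |
| 6 | 364.4 | 394.4/364.4 = 108.2% | 107.7% | 110.2% |

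These are upper values: the excess shrinks as the dosing month runs on. With S = 30 it reaches 10% when 182 + 30.4k = 300, that is k = 3.9, so from month 4 the subject is back below the 110% category. Once all tablets are reconciled, S = 0 and the ratio is 100%.

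**2. Visit 22 supply booked to Core.**

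*Extension-only, completed subject, k months.* Planned: k months. Counted: k − 1 months, because the first month's tablets sit in Core. Compliance = (k − 1)/k: 2/3 = 67% at 3 months, 5/6 = 83% at 6, 23/24 = 95.8% at 24.

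*Core, if the formula is applied there.* Compliance = (182 + S)/182; at 20 mg daily, weekly dose = (182 + S) × 20 / 26.
- S = 28: 115.4%, 4200/26 = 161.5 mg/week
- S = 30: 116.5%, 4240/26 = 163.1 mg/week
- S = 37: 120.3%, 4380/26 = 168.5 mg/week

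The true values are 100% and 140 mg/week. Across this range such a subject crosses into the ≥110% and ≥160 mg/week categories.

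*Sensitivity to dose level.* With a Core average of 140 mg/week (3640 mg in total) and a 30-day Visit 22 supply at weekly dose w, compliance = (3640 + 30w/7)/3640. At Level 1 (w = 20) this is 3725.7/3640 = 102.4%; at Level 6 (w = 280) it is 4840/3640 = 133.0%.

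**3. Visit 22 supply booked to the Extension instead.** Core is 100%, and so is a completed subject's Extension figure. An ongoing subject just after month k then shows up to (k + 1)/k in the Extension-only figure, 4/3 = 133% at 3 months. The phase assignment alone therefore does not settle the ongoing case; a reconciliation cut-off is also needed.

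**The case against.** A reader might infer that the plan will report Core compliance of about 116% for adherent subjects who continue, with a matching inflated Core weekly dose. The documents do not support that. SAP 13.1 leaves both items out of the Core descriptive statistics. They could appear for Core only through the category tables that name no phase, through listing 16.2.5.4, or through a PPS criterion. Nor does the formula say that the Visit 22 supply counts as Core. It is silent, Protocol 7.2.5 dispenses only where applicable, and no document shows how the accountability eCRF assigns that supply.

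A reader might also infer that real under-dosing would be hidden from the PPS decision. By the same arithmetic a true 80% would show as 80 + 16.5 = 96.5%. But SAP 7.3 offers compliance only as an example, with no formula or threshold, and leaves the criteria to be agreed before lock. Protocol 6.4.5 has compliance reviewed at each visit from returned packages, unused drug and the diary. The link to the 13.1 ratio is possible, not stated.

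Further points stand. The tablet count is assumed, and 115% to 120% needs a constant dose in a trial that titrates over six levels. Visit 22 allocation cancels in the combined total once the supply is used or returned. No efficacy endpoint uses the formula, and TEAE proportions use subject counts as denominator.

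What the objection does not remove is the mismatch itself. Planned dose has a Core cut-off and actual dose has none, Extension compliance and weekly dose are planned outputs, and ongoing subjects are expected at the first analysis. For them the stated formula, followed literally, counts tablets in hand as taken.

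**Conclusion.** The point holds as a minor defect in exposure reporting. At the first analysis, combined compliance of a fully adherent ongoing subject is overstated by up to 16.5 percentage points just after Visit 22, 11.0 after 3 Extension months and 8.2 after 6, given a full 30-day supply outstanding and a constant dose. This disappears at final analysis. The boundary error is conditional on booking by dispensing visit: Extension-only compliance of (k − 1)/k for completed subjects, and about 115% to 120% for any Core compliance derived from the formula at constant dose with a supply of 28 to 37 days. The primary FAS result is unaffected. The supportive PPS analysis could be touched only if its compliance criterion, still to be agreed, uses this ratio.

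**What to change.** In SAP 13.1 add rules to this effect:

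1. Tablets dispensed at Visit 22 for Extension use, and their later returns, are assigned to the Extension Phase.
2. For subjects ongoing at the analysis cut-off, the actual dose, and the planned dose and time used as denominators for compliance and average weekly dose, run only to the last visit at which dispensed tablets were reconciled. Tablets dispensed at that visit are excluded.
3. The duration-of-treatment summary is unchanged. It depends only on first and last treatment days and is not affected by dispensing.
4. The section states whether Core compliance and Core weekly dose are tabulated. If a PPS criterion uses compliance, it uses the Core figure under rule 1.

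With these rules the fully adherent subject returns to 3640/3640 = 100% and 140 mg/week in Core, and to 100% in the Extension and combined figures.

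The cost is a few sentences and a date condition in the exposure program; Protocol 6.4.5 already puts dispensed and returned counts on the accountability eCRF. The downside is small: at the first analysis, compliance and weekly dose for ongoing subjects omit up to about one month, and a subject who has not yet reached E1 has no Extension-only ratio.
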